Recruitment will begin in November of 2019. We aim to recruit 25-30 participants to this study via passive recruitment methods. Recruitment flyers will be distributed in community locations such as libraries, grocery stores, community centers, senior centers, and cancer survivor groups. Additionally, oncologists or physicians may refer their patients (cancer survivors) to the study by giving them a study flyer. Faculty and staff from the Division of Epidemiology, Biostatistics, and Preventive Medicine and the UNM Comprehensive Cancer Center will be emailed a copy of the study flyer, provided approval from leadership (i.e., Division Chief, Associate Directors or Program Leaders). The email will briefly explain the study, and indicate a \$5 gift card for one of UNM HSC campus coffee shops will be provided for anyone referring an individual to the study, regardless of final eligibility (referred individual must contact study staff). Upon being contacted, a member of the study team will use a recruitment script to determine level of interest in the study, answer questions and assess eligibility; only trained members of the study team will screen, consent and enroll participants into the study.

20. Provisions to Protect the Privacy Interests of Subjects

The following steps will be taken to secure the data and to maintain participants' privacy:

PROTOCOL TITLE: Southwest Harvest for Health Pilot

Maintaining privacy during recruitment

The recruitment screening process will take place over the phone in a private room. Participants not eligible to participate in the study will be asked if they would like to be added to the future contact database (UNM HRPO IRB Protocol Number 18-629) in order to be made aware of future studies. If their answer is “no” all information about the ineligible participant will be destroyed. If “yes”, their contact information will be added to the secure future contact database and the paper form of the recruitment screener will be held in a locked cabinet indefinitely.

Maintaining privacy during collection of data for study outcomes

Data collection will occur at the participant’s home by trained members of the study team. Note that the Master Gardeners do not collect any data from the study participants.

Maintaining privacy during intervention delivery

The intervention primarily takes place at the participant’s home, i.e., establishing and maintaining a vegetable garden. Participation in study events, such as the Meet & Greet, the Bounty Party, and a visit to a gardening center in the participant’s community, while strongly encouraged, are not required.

21. Economic Burden to Subjects

Participants will have minimal to no economic burden to participate. Investigators will travel to the participants’ homes at the study’s expense and appointments for these home-based visits will be made at the participants’ convenience. Participants will also receive up to four merchandise cards for a total of \$80 (\$20 after each of the three assessments and an optional interview). Gardening and other study supplies will be provided at the study’s expense. However, participants will travel to their local plant store with their Master Gardener Mentor as part of their experience. These merchandise cards may offset any travel costs accrued.

22. Compensation

Participants will receive a \$20 merchandise card to compensate them for their time in completing questionnaires at baseline, mid-study, and follow-up time points (up to \$60 in merchandise cards). Participants who complete an interview at the end of the study will receive an additional \$20 merchandise card. Additionally, participants will receive the gardening supplies needed to begin and maintain three vegetable gardens over the course of the 10-month study. Participants will be allowed to keep these gardening supplies after the study ends (estimated value of \$350) to promote sustainability of the modified health

PROTOCOL TITLE: Southwest Harvest for Health Pilot

behaviors and outcomes. Thus the potential compensation in merchandise cards and gardening supplies could be as high as \$430.

23. Compensation for Research-Related Injury

NA - this research study does not involve more than minimal risk to subjects

24. Consent Process

Notes: (1) Signed informed consent will be obtained on all study subjects. All team members involved in the consent process will have received proper training in human subjects protection. (2) Study team members responsible for screening and recruiting study participants will not have access to private information to identify potential subjects and/or determine eligibility prior to approaching potential subjects for consent. Oncologists and nurse navigators in cancer centers in Bernalillo and Sandoval counties will not be forwarding any PHI to these study team members; instead, potentially eligible cancer survivors will be provided with a study flyer and asked to call the study team to determine eligibility. Therefore, we are not requesting a waiver of consent for screening purposes.

Individuals interested in participating in the study will contact a member of the study team and undergo a screening process to determine eligibility. During this screening process, the participant will be given information about their participation in the study (what the study entails, time commitment, etc.) and opportunities to ask questions. Eligible and interested participants will be mailed a copy of the consent form with a self-addressed stamped envelope. Contact information for the researchers, the Human Research Review Committee, and the Human Research Protections Office will be made available to potential participants.

Within a week of mailing the consent form, a study investigator, trained in the consent process, will review the consent form with the individual over the phone. The following questions will be asked to assess the subjects' understanding of the consent process. Do you have any questions about the study? We have covered a lot of information. Could you please describe for me what you think participating in this study requires? Do you have the toll free study telephone number? The subject may decline participation in the study or drop out of the study at any time. This will be stated both verbally (phone call) and in writing (consent form). Once a signed copy of the consent form is received by the study team, the participant will be enrolled in the study and the baseline home visit will be scheduled.

While interviews are covered in the currently approved consent form, we wish to provide compensation for completion of an optional interview (a \$20 merchandise card). We request a waiver of signed consent for the interview, as no name or personally identifiable information will be included. Please see the Informed Consent Cover Letter, which will be sent to a sample (8-12) of study participants (aka cancer survivors).

PROTOCOL TITLE: Southwest Harvest for Health Pilot

For the duration of the study, the volunteer Master Gardeners mentor a cancer survivor in home vegetable gardening. At the end of the intervention, we wish to administer a questionnaire to the Master Gardeners, to obtain their feedback on the study. A sample of Master Gardeners indicating interest, will be invited to complete a telephone or Zoom interview to provide feedback in greater detail. We request a waiver of signed consent for participation in the voluntary questionnaire and interview. The personally identifiable information (name, telephone number, email address) from the questionnaire will only be used to determine which Master Gardeners are interested in completing an interview. All identifying information will be removed from the questionnaire prior to storage and analysis. No names or personal identifiers will be included in the audio recording of the interview.

25. Documentation of Consent

Participants will have ample opportunity to review the consent form, ask questions, and review the form with a trained study team member. A signed consent form will be mailed to the study team in a self-addressed stamped envelope. The participant will retain a copy of the signed consent form to keep for their records.

While we are requesting a waiver of signed consent for the post-intervention interviews (and questionnaire for Master Gardeners), participants will receive a copy of the consent cover letter for their records.

26. Study Test Results/Incidental Findings

NA - Individual results and incidental findings will not be shared with participants

27. Sharing Study Progress or Results with Subjects

Aggregate data from this study will be published in peer-reviewed journals and presented at local and national conferences.

28. Inclusion of Vulnerable Populations

NA – this study is not enrolling individuals from vulnerable populations.

29. Community-Based Participatory Research

NA - This is not a community-based participatory research project

30. Research Involving American Indian/Native Populations

While the proposed project does not exclude individuals identifying as Native American, American Indian and Native Populations will not be directly targeted for recruitment to the study.

31. Transnational Research

NA - This is not a transnational study.

32. Drugs or Devices

NA - this research does not evaluate the safety or effectiveness of a medical device

The activPAL3 activity monitoring device (worn on the thigh):

- a. This is not a device study, i.e., this study does not evaluate the efficacy or safety of a device. There is no information on the FDA website regarding the activPAL3 monitor (NOTE: these monitors are from a company in Scotland, UK). However, these monitors are similar to the ActiGraph monitors except for the attachment method. The activPAL3 monitors are not investigational devices as they are commercially available (<http://www.paltechnologies.com/>); the shipment of activPAL3 monitors was cleared by the FDA and delivered to the Study PI. These monitors are the gold standard for objectively measuring sedentary behavior and ambulation in research study participants and have been used in many trials in the U.S. The activPAL3 monitors are more expensive than consumer wearable monitors (e.g., FitBit, Jawbone) and require special software to analyze the data, thus these monitors are used in research rather than being purchased by consumers. In this study, the monitors are used to measure outcomes (frequency, duration, and intensity of free-living sedentary behavior and light physical activity), and are not used to diagnosis or treat disease, or to support/sustain life.
- b. These monitors do not present a potential for serious risk to the health, safety, or welfare of the subject. There is a potential for a small risk of skin irritation due to the adhesive used to attach the activPAL3 to the thigh. We are minimizing this risk by asking the research participants to check the monitors daily and if skin irritation occurs, to remove the monitor and contact study staff.

To our knowledge, the FDA has not evaluated this device; however, it would likely fall under the same category as a similar research grade activity monitor, ActiGraph (not used in this study). We believe, that like the ActiGraph monitors, the activPAL3 monitors used in this study poses non-significant risk per the FDA definition: i) it is not an implanted device, ii) it is not a life sustaining/ supporting device, iii) it is not “for a use of substantial importance in diagnosing, curing, mitigating, or treating disease, or otherwise preventing impairment of human health”, and iv) it does not otherwise present “a potential for serious risk to the health safety, or welfare of a subject”.

33. Principal Investigator's Assurance

By submitting this study in the Click IRB system, the principal investigator of this study confirms that:

- The information supplied in this form and attachments are complete and correct.
- The PI has read the Investigator's Manual and will conduct this research in accordance with these requirements.
- Data will be collected, maintained and archived or destroyed per HSC Data Security Best Practices, including:
 1. **Best Practice for data collection** is for it to be directly entered onto a data collection form that is in a secured access folder on an HS drive behind a firewall, or in a secure UNM Data Security approved system such as RedCap.
 2. **Data collection of de-identified data**, if done in a clinical setting or other setting that does not allow direct entry into a secured system, may be done temporarily using a personal or university owned electronic storage device or hard copy document. **The important security safeguard is that no identifiers be include if the data is entered or stored using an untrusted device or storage.**
 3. **Permanent (during data analysis, after study closure)** storage must reside on HSC central IT managed storage. Processing of data (aggregation, etc.) are to be carried out in such a way as to avoid creating/retaining files on untrusted storage devices/computers. Trusted devices are HSC managed and provide one or more of following safeguards: access logs, encryption keys, backups, business continuity and disaster recovery capabilities.
 4. **Alternate storage media** must be approve by HSC IT Security as meeting or exceeding HSC central IT provided security safeguards.

Checklist Section

This section contains checklists to provide information on a variety of topics that require special determinations by the IRB. Please complete all checklists relevant to your research.

47. Data Transfer/Sharing (Checklist)

Complete this checklist if the research involves transferring/sharing of data with an external entity (institution, company, etc.).

A. Will data be transferred/shared with an external entity (institution, company, etc.)?

Yes

No. **The remainder of this section does not apply.**

B. Indicate if the data is incoming and/or outgoing:

C. Provide the name of the entity that data will be transferred/shared with:

D. Provide the contact name, email and phone number with whom data is being transferred/shared with:

E. Who is responsible for transmission of the data?

F. Who is responsible for receiving the data?

G. Describe how the data will be transferred/shared. Please note data cannot be transferred/shared without assistance from UNM HSC IT. **Requesting HSC Central IT Transfer is detailed on the Sponsored Projects website:**

H. For data being transferred/shared with outside locations or entities, describe the following:

- Where is data storage and how will it be maintained in a secure manner (i.e. encryption, password protection, use of Qualtrics or REDCap, etc)?
- What is method in which data will be collected and stored (i.e. electronic, hard copy, etc)?
- How long will the data be stored?
- Who will have access to data?

I. Please list all specific data elements, variables, etc. to be sent out and/or received. Indicate if the data contains identifiers and health information. Please note that identifiers that MUST be removed to make health information de-identified are as follows: Names, All geographic subdivision smaller than a State, All elements of year (except year), Telephone, Fax numbers, E-mail addresses, Social Security, Medical record number, Health plan beneficiary, Account numbers, Certificate/license numbers, Vehicle identifiers and serial numbers, Device identifiers and serial numbers, Web URLs, IP address numbers, Biometric identifiers, full face photographic images, and Any other unique identifying number, characteristic or code.)

J. If the research requires the access, use, or disclosure of any of the 18 individually identifiable protected health information (PHI) identifiers that can be used to identify, contact, or locate a person (e.g., name, medical record number, etc.), are the subjects going to consent to or authorize the disclosure of their individually identifiable health information?

a. **Or** is HIPAA authorization altered or waived?

PROTOCOL TITLE: Southwest Harvest for Health Pilot

- K. What is the classification of the data (de-identified, limited data set, protected health information, other).
- L. Does the request to transfer/share data include clinical data that belongs to the UNM Health Systems?
- M. Does the data to be transferred/shared include information about patients seen at external health system or at a third party medical provider?
- N. Is the external entity a “covered entity”?
- O. Is the data that is going to be transferred/shared owned or partially owned by another party or have any type of restrictions including regulatory restrictions (i.e. HIPAA, FERPA, etc.)?
- P. Is the data publically available? If yes, please provide details:
- Q. Does the data include information about substance abuse treatment, sexually transmitted diseases, genetic testing results, HIV/AIDS testing results, and/or mental health?

48. Specimen Transfer/Sharing (Checklist)

Complete this checklist if the research involves transferring/sharing of specimens with an external entity (institution, company, etc.).

- A. Will specimens be transferred/shared with an external entity (institution, company, etc.)?
 - Yes
 - No. **The remainder of this section does not apply.**
- B. Indicate if the specimens are incoming and/or outgoing:
- C. Provide the name of the entity that specimens will be being transferred/shared with:
- D. Provide the contact name, email and phone number with whom specimens are being transferred/shared with:
- E. Who is responsible for sending out the specimens? Please note specimens cannot be sent out without a fully executed material transfer agreement.
- F. Who is responsible for receipt of the specimens? Please note specimens cannot be received without a fully executed material transfer agreement.
- G. For specimens being transferred/shared with outside locations or entities, describe the following:
 - *Where is specimen storage and how will it be maintained in a secure manner?*
 - *What is method in which specimens will be collected and stored?*

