Study Timeline: August 2019 – July 2021																		
	2019				2020										2021			
Month	A	N	J	F	M	A	M	J	J	A	S	O	N	D	J	M	M	J
-	-	O	D												-	-	-	
Development																		
Recruitment																		
Intervention delivery																		
Data cleaning/prep																		
Analyses																		
Publications																2		
Grant Submissions																	4	

¹ Study protocol paper

² Study outcomes paper

³ Initial R01 submission

⁴ Revised R01 submission

6. Study Endpoints

Primary and secondary study endpoints

The primary aim is to adapt the Harvest for Health intervention to the multi-cultural population of cancer survivors and for the local context (physical, social, and cultural environment) of New Mexico. The endpoint is systematic documentation of the adaptation process using a recommended framework.

Other endpoints are to assess the feasibility and acceptability of the “Southwest Harvest for Health” mentored gardening program through recruitment and retention rates, adherence/fidelity to the intervention, and acceptability of the program for both cancer survivors (participants) and Cooperative Extension Master Gardeners.

Secondary endpoints include estimates on pre-post changes in vegetable servings per day, physical activity, sleep quality, physical functioning and performance, and hrQOL. Pre-post change data will inform the sample size for the future, larger study.

Primary and secondary safety endpoints

Gardening could result in cuts or scrapes which could expose the participant to bacteria in the soil or exacerbate lymphedema. Cancer survivors for whom gardening activities could pose excess risk will be excluded from the study.

Additionally, gardening involves a variety of movements, i.e., bending, kneeling, stooping, getting up and down, and other light-to-moderate intensity physical activity, which could result in soreness, stiffness, and other potential issues (e.g., sunburn) if substantially different than the participants’ normal daily activities. To mitigate these issues, participants will receive a notebook containing information on gardening safety, e.g., protecting knees and back, sun protection, etc.

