All adverse events associated with the performance tests will be tracked. The performance tests incorporate movements typically undertaken during normal daily activities (standing from a chair, walking a short distance, sitting on a chair, lifting a light object, etc.), and thus represent tests that are more likely to be safely performed. One or more members of the study team will be present in the participant’s home during the performance tests. Safety checks will be made prior to the performance tests.

Exploratory endpoints

There are no exploratory endpoints.

7. Research Setting

This is a home-based intervention. The garden will be located at the participant’s home. Members of the UNM study team will visit the participant at their home on three separate occasions (baseline, mid-point, follow-up) during the study to assess health behaviors and outcomes. Study staff will also verify inclusion criteria specific to gardening, i.e., absence of an existing vegetable garden, adequate space, sun and running water to accommodate a successful home vegetable garden.

PROTOCOL TITLE: Southwest Harvest for Health Pilot

Recruitment flyers will be distributed in community locations such as libraries, grocery stores, community centers, senior centers, and cancer survivor support groups.

Study staff will be housed in the Cancer Research Facility, where recruitment and screening will take place.

COVID-19 Modifications

Due to COVID-19, the mid-point and final assessment of health behaviors and outcomes will be conducted remotely (i.e., via mailed and telephone-administered surveys) rather than home visits.

8. Resources Available

Study Personnel

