Due to COVID-19, the mid-point and final assessment of health behaviors and outcomes will be conducted remotely (i.e., via mail and telephone-administered surveys) rather than home visits.

Availability of Medical or Psychological Resources

This is a minimal risk study; thus these resources will not be made available. The participant will continue to have access to their general practitioner and oncologists as per usual care.

Study Protocol, Research Procedures, and Duties and Functions

The finalized protocol and research procedures will be distributed to all persons assisting with the research. In addition, meetings will be held with team members to review the specific duties and functions of each member.

9. Prior Approvals

Departmental scientific review and approval was obtained on 10/15/2019 and assigned as protocol INST UNM 1905.

10. Multi-Site Research

NA - this is a single-site study.

11. Study Procedures

The proposed study includes three visits to the participant's home, a mentored-gardening intervention and follow-up telephone interview.

1. Home visits: Home visits to assess study outcomes will occur three times over the study period: baseline (within one month of beginning the intervention), mid-intervention (around 6 months) and post-intervention (at 10 months). Two members of the SWH4H study team will visit the participant at their residence to assess the participant's health status such as their height, weight, and waist size and physical function through a series of physical performance tests (i.e. walking speed, ability to rise from a chair). These home visits will take 45-60 minutes each. In addition to home visits, participants will be mailed questionnaires approximately 10 days prior to their baseline and follow-up home visits. These questionnaires will be collected by study investigators upon arrival. Questionnaires will assess the following:
 - a. Participant characteristics: Data will be collected on age, race/ethnicity, education, income range, marital status, occupation, and smoking status. Cancer related data will be obtained via self-report from participants (treatment (yes/no): surgery, radiotherapy, chemotherapy, hormone therapy; diagnosis year; cancer type).
 - b. Lifestyle behaviors: Participants will also be asked to complete questionnaires about their vegetable and fruit intake (servings per day), physical activity, sedentary behavior, physical function, sleep-behaviors, health, and quality of life.

Anthropometrics

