Participants will be asked to wear the activPAL3, an electronic activity monitor, for the objective assessment of sedentary activity and physical activity. The small, thin device (like a patch) will be worn on their mid-thigh (day and overnight) for 7 days

PROTOCOL TITLE: Southwest Harvest for Health Pilot

at the beginning, at 6 months, and at the end of the study. This is not a tracking device. The activity monitor will record general movement (sitting, standing, and stepping) and will enable us to get a better idea of the participant's daily activity and inactivity levels (versus self-report alone). We will also provide participants instructions for applying and removing the monitor. The activPAL3 monitor will be collected during the home visits for additional outcome assessment. Note: The activPAL3 is attached to the thigh using Tegaderm Dressing (a transparent dressing/tape; see Tegaderm Dressing.PDF uploaded under Local Site Documents – Other Attachments).

Mediators

Community-Level: Participant-MG dyads will independently assess the participant's local environment for support of vegetable gardening considering the following factors: 1) availability of garden stores; 2) presence of pests (i.e., insects, deer); 3) neighborhood covenants that impose landscaping restrictions; and 4) sense of belonging with other gardeners in local community.

Interpersonal: We will use the Social Support & Eating Habits (10 items) & Exercise Surveys.

Individual: This assessment will measure the participant's self-efficacy (survivors' beliefs in their ability to maintain a successful vegetable garden).

COVID-19 Modifications

The following modifications will be made to the mid-point and final (post-intervention) assessment of study outcomes due to COVID-19.

The visit by study investigators to the participant's home will be replaced with remote methods (mail and telephone) in order to avoid any in-person contact between members of the study team and participants in an indoor setting.

Due to this change (from home visit to mail/telephone), the following aspects of data collection will also require change:

- Collect self-reported weight
- Skip all objective measures of physical functioning (i.e., physical performance). Note that while some research studies are moving to a remote assessment of physical performance, this study does not have the resources to be able to collect this type of data remotely at this time.

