- Administer the Fruit & Vegetable Dietary Intake (Using same EATS survey) over the phone rather than in-person. The food models will be replaced with "show cards" that include the frequency of intake and some example portion sizes to help the participant more accurately report the amount consumed. The show cards will be included in a sealed envelope to be opened during the phone call. Otherwise,

PROTOCOL TITLE: Southwest Harvest for Health Pilot

seeing the dietary questions could influence the participants eating behaviors during the week prior to the phone assessment.

- Self-reported physical activity (using same Godin Leisure Time Physical Activity Questionnaire) will be administered over the phone to improve the accuracy of reporting.

2. Gardening Intervention: Cancer survivors (participants) will be paired with a certified Master Gardener from the Albuquerque Area Cooperative Extension or Sandoval County Extension who will mentor the participants in planting and tending to three seasonal vegetable gardens throughout the year (spring, summer and fall)

- a. Participants will be invited to attend a meet-and-greet event where they will meet their Master Gardener mentor and members of the study team in person. This meeting will provide the study participants the opportunity to pick up their gardening supplies and communicate the best days/times to meet with their Master Gardener mentors.
- b. Supplies needed to begin the participants' home vegetable gardens will be picked-up by participants at the meet-and-greet event and/or delivered to their homes. These include but are not limited to: soil, plants, seeds, and fertilizer to support either 4 container-style garden boxes (which can be used to garden on balconies, patios or decks) or 1 raised bed garden (equivalent square footage). These supplies will be provided free of charge.
- c. The Master Gardener mentors will help guide the study participants in setting-up the garden, maintaining it, and replanting it season-to-season.
- d. In providing this support, the Master Gardener mentors will make monthly visits to participants' home and will also speak with them over the phone or communicate with them via email on a monthly basis to check-in on how they are doing with their gardens (e.g. troubleshoot issues or offer advice)

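### The physical activity endpoint names no instrument, the self-report appears to change mode after baseline, and the monitor has no stated return route once home visits stop

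*Combined protocol and SAP*

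**What the plan says.** **Endpoint.** Section 6 reads: "Secondary endpoints include estimates on pre-post changes in vegetable servings per day, physical activity, sleep quality, physical functioning and performance, and hrQOL". It adds: "Pre-post change data will inform the sample size for the future, larger study". Aim 3 and Section 12.1 are equally general, and Section 12.1 leaves its list of outcomes open-ended. None of the three gives an instrument, variable or unit for physical activity.

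**Instruments.** Section 11 collects physical activity in two ways: the Godin Leisure Time Physical Activity Questionnaire (self-report at three intensity levels) and the activPAL3, worn for 7 days at baseline, 6 months and end of study "for the objective assessment of sedentary activity and physical activity". The PACE questionnaire covers sedentary behavior by self-report.

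**Mode of the self-report.** Section 11, item 1, says that "participants will be mailed questionnaires approximately 10 days prior to their baseline and follow-up home visits", and it includes physical activity among the topics. The COVID-19 modifications in the same section apply to mid-point and final only. Under them the Godin "will be administered over the phone to improve the accuracy of reporting".

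**Monitor logistics.** Section 11 has the activPAL3 collected at home visits. The COVID-19 modifications replace the mid-point and final visits by mail and telephone. Sections 7 and 8 describe those remote assessments as surveys.

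**Sedentary behavior.** Section 32 says that "the monitors are used to measure outcomes (frequency, duration, and intensity of free-living sedentary behavior and light physical activity". Section 6 does not list sedentary behavior, and it states: "There are no exploratory endpoints".

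**The concern.** With two instruments collected and neither designated, the endpoint can be chosen after both results are known. The two are also not equally placed. The stated reason for moving the Godin to telephone is better accuracy, which concedes that the mode affects the answer. Section 2 specifies a single arm, so no comparison group undergoes the same mode change, and a shift in reporting cannot be separated from a change in activity.

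What is at stake is the use of the result. Sections 6 and 12 give the pre-post changes the job of informing the size of the future trial. A Godin change that carries a mode artefact would pass it into that calculation.

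**Working it through.** The plan gives no power analysis, effect size or SD for this endpoint, so there is no figure to reproduce. The check is mainly textual, followed by one illustration.

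**1. Is a measure named?** No. Aim 3, Section 6 and Section 12.1 name the concept, and Section 11 supplies two instruments for it.

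**2. Does the Godin mode change?** Item 1 of Section 11 indicates a form mailed before the baseline visit and collected on arrival. The COVID-19 modifications give telephone administration at mid-point and final. One caution applies: fruit and vegetable intake is in the same mailed list, yet the modifications describe the EATS screener as in-person before the change. The mailed list is therefore not a sure guide, and the baseline mode of the Godin needs confirming. Even so, the Godin sits in the list of data collection steps that had to change, which points to a change of mode from either starting point.

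**3. Is the monitor unaffected?** Only its wear schedule is. Its collection depended on visits that were replaced, and no substitute route is stated. The documents neither confirm nor exclude follow-up monitor data.

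**4. Do Sections 6 and 32 agree on sedentary behavior?** No. Section 32 treats it as an outcome; Section 6 omits it.

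**5. Could the study detect a mode shift?** The 95% CI half-width for a mean change, in SD units, is t(0.975, n−1)/√n. With n = 20 (80% of 25) it is 0.47; with n = 30 it is 0.37. A shift of a few tenths of an SD is within the noise. Even a precise estimate would not separate it from a real change.

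**6. What could it do to the future trial?** All values here are assumptions: a two-arm 1:1 trial, two-sided alpha 0.05, 80% power, true standardised effect 0.3, and the observed pre-post change used as the between-arm difference.

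- Per-arm size: n = 2(1.960 + 0.842)²/d² = 15.70/d², where d = 0.3 + mode shift, rounded up.
- Real power: Φ(0.3·√(n/2) − 1.960).

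| Mode shift (SD) | Observed d | n per arm | Real power |
|---|---|---|---|
| −0.1 | 0.2 | 393 | 99% |
| 0 | 0.3 | 175 | 80% |
| +0.1 | 0.4 | 99 | 56% |
| +0.2 | 0.5 | 63 | 39% |
| +0.3 | 0.6 | 44 | 29% |

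The table shows sensitivity to a shift. It is not evidence that a shift of any given size occurred.

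**The case against.** **Limited stakes.** This is a secondary, estimation-only outcome in a feasibility study of 25 to 30 people whose primary endpoint is documentation of the adaptation process. No test is planned for it. That stands and limits the severity. It does not remove the point, because the plan assigns the estimate a later use.

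**Uncertain baseline mode.** The mailed reading is an inference. That stands, and the fix includes confirming it. If the Godin was asked face to face at baseline, the shift would be from in-person to telephone.

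**Unknown direction.** Better accuracy could lower reported activity and hide a gain as easily as create one. That stands. A reader might infer that the Godin will overstate benefit; the documents do not support a direction.

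**The monitor as a clean substitute.** A reader might infer that the activPAL3 gives a follow-up measure unaffected by the COVID-19 changes. The documents support this for the wear schedule only.

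**Sedentary time.** A reader might infer that it is the monitor's chief product and has no endpoint status. Section 11 gives the monitor two purposes, and Section 32 calls sedentary behavior an outcome. The supportable finding is that the two sections do not match.

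**Same-mode Godin change.** Comparing mid-point with final, both by telephone, may look like a way out. It has no pre-intervention value, so it cannot replace the pre-post change in Aim 3. It also compares August with November.

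**Conclusion.** The point holds in a limited form. Physical activity is an endpoint without a named measure. One of its two candidate sources appears to change mode after baseline, in a design that cannot separate mode from intervention. The other keeps its wear schedule but has no stated route for sending or returning devices at the two follow-up times. Separately, Sections 6 and 32 disagree on sedentary behavior.

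The size and direction of any mode effect are unknown. The range of 44 to 393 per arm, against 175, rests wholly on the assumed true effect of 0.3 SD and shifts of −0.1 to +0.3 SD. The conclusion about the Godin depends on its baseline mode differing from telephone, which the text indicates but does not settle. The matter should be corrected before analysis; it does not affect the feasibility endpoints.

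**What to change.** 1. Before analysis, name one activPAL3 activity variable, with its unit, as the physical activity endpoint in Aim 3, Section 6 and Section 12. Which variable is for the study team to justify; much of the gardening movement described in Section 6 is bending and kneeling rather than stepping.
2. In Section 11, state how monitors are sent and returned at mid-point and final, for example by mail.
3. Confirm the baseline mode of the Godin. Report its pre-post change as supportive only, with the mode at each time stated and a caution against using it alone to size the future trial.
4. If follow-up monitor data do not exist, say so, and report the Godin change as confounded with mode.
5. Align Sections 6, 11 and 32: either list sedentary behavior as a secondary endpoint with its source named, or stop calling it an outcome.

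The cost is mostly wording, since monitor wear is already planned, plus postage if devices go by mail. The downside is that participants without valid or returned monitor data drop out of the endpoint, so the number contributing should be reported.
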